7.2.2.5.8 Virology

Virology panel outlined in [Table 7-4](#) will be performed as per the assessment schedule in [Table 7-1](#).

7.2.2.6 Cardiac assessments

7.2.2.6.1 Electrocardiogram (ECG)

A standard 12 lead ECG will be performed as per the assessment schedule in [Table 7-1](#) and [Table 7-5](#). Blood samples scheduled at the same time point should be taken after the ECGs are completed. The ECGs on C1D1, and C4D1 must be performed in triplicate. For the Screening, EOT and Unscheduled visits only one ECG per visit is required.

Table 7-5 Local ECG collection plan

Cycle	Day	Time
Screening	-21 to -1	Anytime
1	1	*Pre-dose (0 hr)
1	1	*1hr (±5 min) hour post last treatment administration
4	1	*Pre-dose
4	1	*1hr (±5 min) hour post last treatment administration
EOT	-	Anytime
Unscheduled**	-	Anytime

* ECGs performed in triplicate at these PK matched timepoints only.
** A PK sample should be collected just after an ECG was performed due to an unexpected cardiac signal.

Interpretation of the tracing must be made by a qualified physician and documented on the ECG CRF page. Each ECG tracing should be labeled with the study number, patient initials (where regulations permit), patient number, date, and kept in the source documents at the study site. Clinically significant abnormalities present at screening should be reported on the Medical History CRF page. Clinically significant findings must be discussed with Novartis prior to enrolling the patient in the study. New or worsened clinically significant findings occurring after informed consent must be recorded on the Adverse Events CRF page.

7.2.2.6.2 Cardiac and skeletal muscle markers.

Due to known asymptomatic creatine kinase elevations associated with MCS110, additional labs will be analyzed to rule out cardiac muscle damage (CK-MB and Troponin I/T) or skeletal muscle damage (aldolase, myoglobin or other skeletal muscle marker per local guidelines). The muscle damage markers will be measured at baseline and anytime during the study in case of CK elevation ≥ 5 x ULN.

7.2.2.7 [For Japan only] Radiological examinations

7.2.2.7.1 Chest x-ray

A 2-view chest x-ray will be performed at screening and Day 8 of Cycle 1.

7.2.3 Pharmacokinetics and immunogenicity assessments

PK profiles to assess PK properties of MCS110 and PDR001 will be collected from all enrolled patients. However, only the patients from Phase Ib part will have additional PK collected on day 2, 4 and 15.

Immunogenicity (IG) samples will also be collected to monitor appearance of anti-drug antibodies directed against MCS110 or PDR001. Please refer to [Table 7-6](#) and [Table 7-7](#) for details on PK and IG sample collections.

If the dosing of Cycle 4 Day 1 is delayed, the PK sampling for the full PK profile should be delayed accordingly to match the scheduled time points for Cycle 4 as outlined in [Table 7-6](#) and [Table 7-7](#). After the primary CSR data cut-off date is reached, no additional PK and IG samples will be collected for the patients still on-going on the study.

Table 7-6 Phase Ib Part: Pharmacokinetic blood collection log for MCS110, PDR001 and IG samples

Cycle	Study day	Analytes	Scheduled time point (Sampling window)	Total volume of Blood sample
1	1	MCS110, PDR001 and IG ^a	Pre-dose ^b (0 hr)	6 mL
1	1	MCS110, PDR001	1 hr (± 5 min) post end of C1D1 infusion dose ^c	4 mL
1	2	MCS110, PDR001	24 hr (± 2 hr) post dose	4 mL
1	4	MCS110, PDR001	72 hr (± 6 hr) post dose	4 mL
1	8	MCS110, PDR001	168 hr (± 8 hr) post dose	4 mL
1	15	MCS110, PDR001	336 hr (± 8 hr) post dose	4 mL
2	1	MCS110, PDR001 and IG ^a	Pre-dose ^b of cycle 2 (0 hr)	6 mL
3	1	MCS110, PDR001 and IG ^a	Pre-dosed ^b of cycle 3 (0 hr)	6 mL
4	1	MCS110, PDR001 and IG ^a	Pre-dose ^b of cycle 4 (0 hr)	6 mL
4	1	MCS110, PDR001	1 hr (± 5 min) post end of C4D1 infusion dose ^c	4 mL
4	2	MCS110, PDR001	24 hr (± 2 hr) post dose of cycle 4	4 mL
4	4	MCS110, PDR001	72 hr (± 6 hr) post dose of cycle 4	4 mL
4	8	MCS110, PDR001	168 hr (± 8 hr) post dose of cycle 4	4 mL
4	15	MCS110, PDR001	336 hr (± 8 hr) post dose of cycle 4	4 mL
5	1	MCS110, PDR001 and IG ^a	Pre-dose ^b of cycle 5 (0 hr)	6 mL
6	1	MCS110, PDR001 and IG ^a	Pre-dose ^b of cycle 6 (0 hr)	6 mL
EOT		MCS110, PDR001 and IG ^a		6 mL

Cycle	Study day	Analytes	Scheduled time point (Sampling window)	Total volume of Blood sample

Blood samples are to be collected from the arm opposite from infusion site, or alternatively, infusion site will need to be flushed with 10 mL of saline.
 
^a Immunogenicity (IG) (Anti-Drug [MCS110 or PDR001] Antibody): blood samples to be collected for anti-drug antibody together with PK samples
 
^b Pre-dose blood samples should be collected prior to start of infusion of any treatment
 
^c MCS110 sampling time is relative to the end of MCS110 infusion; PDR001 sampling time is relative to the end of PDR001 infusion
				

Table 7-7 Phase II Part: Pharmacokinetic blood collection log for MCS110, PDR001 and IG samples

Cycle	Study day	Analytes	Scheduled time point (Sampling window)	Total volume of Blood sample
1	1	MCS110, PDR001 and IG ^a	Pre-dose ^b (0 hr)	6 mL
1	1	MCS110, PDR001	1 hr (\pm 5 min) post end of C1D1 infusion dose ^c	4 mL
1	8	MCS110, PDR001	168 hr (\pm 8 hr) post dose	4 mL
2	1	MCS110, PDR001 and IG ^a	Pre-dose ^b of cycle 2 (0 hr)	6 mL
3	1	MCS110, PDR001 and IG ^a	Pre-dosed ^b of cycle 3 (0 hr)	6 mL
4	1	MCS110, PDR001 and IG ^a	Pre-dose ^b of cycle 4 (0 hr)	6 mL
4	1	MCS110, PDR001	1 hr (\pm 5 min) post end of C4D1 infusion dose ^c	4 mL
4	8	MCS110, PDR001	168 hr (\pm 8 hr) post dose of cycle 4	4 mL
5	1	MCS110, PDR001 and IG ^a	Pre-dose ^b of cycle 5 (0 hr)	6 mL
6	1	MCS110, PDR001 and IG ^a	Pre-dose ^b of cycle 6 (0 hr)	6 mL

Blood samples are to be collected from the arm opposite from infusion site, or alternatively, infusion site will need to be flushed with 10 mL of saline.
 
^a Immunogenicity (IG) (Anti-Drug [MCS110 or PDR001] Antibody): blood samples to be collected for anti-drug antibody together with PK samples
 
^b Pre-dose blood samples should be collected prior to start of infusion of any treatment
 
^c MCS110 sampling time is relative to the end of MCS110 infusion; PDR001 sampling time is relative to the end of PDR001 infusion
				

7.2.3.1 Analytical method

[figure not shown]
Bioanalysis for pharmacokinetic samples will employ the following validated assays:

[figure not shown]
1. The assay to quantify MCS110 will be a validated ELISA assay.
2. The assay to quantify PDR001 will be a validated LCMS assay.
3. The assay to quantify and assess the anti-MCS110 antibody will be a validated homogeneous ELISA.
4. The assay to quantify and assess the anti-PDR001 antibody will be a validated homogeneous ELISA.

[figure not shown]
7.2.3.2 PK and immunogenicity sample handling, labeling, and shipping instructions

A total of 4 mLs of blood will be collected at each time point for MCS110 and PDR001 PK. After clotting and centrifugation, the resulting serum will be separated into 6 aliquots (3 for MCS110 and 3 for PDR001) and will be stored frozen until analysis. For time points when MCS110 and PDR001 PK and IG for both molecules are to be measured, a total of 6 mLs of blood will be collected at each time point. The samples will be prepared as serum and will be aliquoted into 12 aliquots (3 aliquots for each analyte MCS110 PK, PDR001 PK, MCS110 IG and PDR001 IG). Blood samples should be collected from the arm opposite from the investigational drug infusion, or from another site. Please see the [\[Laboratory Manual\]](#) for detailed instructions about collection, handling and shipment of samples.

The actual collection date and time of each sample will be entered on the Pharmacokinetics/Immunogenicity Blood Collection eCRF pages.

8 Safety monitoring and reporting

8.1 Adverse events

8.1.1 Definitions and reporting

An adverse event is defined as the appearance of (or worsening of any pre-existing) undesirable sign(s), symptom(s), or medical condition(s) that occur after patient's signed informed consent has been obtained.

Abnormal laboratory values or test results occurring after informed consent constitute adverse events only if they induce clinical signs or symptoms, are considered clinically significant, require therapy (e.g., hematologic abnormality that requires transfusion or hematological stem cell support), or require changes in study medication(s).

Adverse events that begin or worsen after informed consent should be recorded in the Adverse Events CRF. Conditions that were already present at the time of informed consent should be recorded in the Medical History page of the patient's CRF. Adverse event monitoring should be continued for 150 days after the last dose of PDR001 or 90 days after the last dose of MCS110 for patients who stopped PDR001 and continued MCS110 alone for more than 60 days).

After initiation of new post-treatment antineoplastic therapy, only AEs suspected to be related to study treatment will be collected in the Adverse Events CRF.

Adverse events (including lab abnormalities that constitute AEs) should be described using a diagnosis whenever possible, rather than individual underlying signs and symptoms. When a clear diagnosis cannot be identified, each sign or symptom should be reported as a separate Adverse Event.

Adverse events will be assessed according to the Common Terminology Criteria for Adverse Events (CTCAE) version 4.03. If CTCAE grading does not exist for an adverse event, the severity of mild, moderate, severe, and life-threatening, corresponding to Grades 1 - 4, will be used. CTCAE Grade 5 (death) will not be used in this study but is collected as a seriousness criteria; rather, information about deaths will be collected through a Death form.

The occurrence of adverse events should be sought by non-directive questioning of the patient (subject) during the screening process after signing informed consent and at each visit during the study. Adverse events also may be detected when they are volunteered by the patient (subject) during the screening process or between visits, or through physical examination, laboratory test, or other assessments. As far as possible, each adverse event should be evaluated to determine:

- The severity grade (CTCAE Grade 1-4)
- Its duration (Start and end dates)
- Its relationship to the study treatment (Reasonable possibility that AE is related: No, Yes)
- Action taken with respect to study or investigational treatment (none, dose adjusted, temporarily interrupted, permanently discontinued, unknown, not applicable)
- Whether medication or therapy was given (no concomitant medication/non-drug therapy, concomitant medication/non-drug therapy)
- Outcome (not recovered/not resolved, recovered/resolved, recovering/resolving, recovered/resolved with sequelae, fatal, unknown)
- Whether it is serious, where a serious adverse event (SAE) is defined as in [Section 8.2.1](#) and which seriousness criteria have been met.

All adverse events should be treated appropriately. If a concomitant medication or non-drug therapy is given, this action should be recorded on the Adverse Event CRF.

Once an adverse event is detected, it should be followed until its resolution or until it is judged to be permanent, and assessment should be made at each visit (or more frequently, if necessary) of any changes in severity, the suspected relationship to the study treatment, the interventions required to treat it, and the outcome.

Progression of malignancy (including fatal outcomes), if documented by use of appropriate method (for example, as per irRC or as per RECIST), should not be reported as a serious adverse event.

Adverse events separate from the progression of malignancy (example, deep vein thrombosis at the time of progression or hemoptysis concurrent with finding of disease progression) will be reported as per usual guidelines used for such events with proper attribution regarding relatedness to the drug.

8.1.2 Laboratory test abnormalities

8.1.2.1 Definitions and reporting

Laboratory abnormalities that constitute an Adverse event in their own right (are considered clinically significant, induce clinical signs or symptoms, require concomitant therapy or require changes in study treatment), should be recorded on the Adverse Events CRF. Whenever possible, a diagnosis, rather than a symptom should be provided (e.g. anemia instead of low hemoglobin). Laboratory abnormalities that meet the criteria for Adverse Events should be followed until they have returned to normal or an adequate explanation of the abnormality is found. When an abnormal laboratory or test result corresponds to a sign/symptom of an already reported adverse event, it is not necessary to separately record the lab/test result as an additional event.

Laboratory abnormalities, that do not meet the definition of an adverse event, should not be reported as adverse events. A Grade 3 or 4 event (severe) as per CTCAE does not automatically indicate a SAE unless it meets the definition of serious as defined below and/or as per investigator's discretion. A dose hold or medication for the lab abnormality may be required by the protocol in which case the lab abnormality would still, by definition, be an adverse event and must be reported as such.

8.2 Serious adverse events

8.2.1 Definitions

Serious adverse event (SAE) is defined as one of the following:

- Is fatal or life-threatening
- Results in persistent or significant disability/incapacity
- Constitutes a congenital anomaly/birth defect
- Is medically significant, i.e., defined as an event that jeopardizes the patient or may require medical or surgical intervention to prevent one of the outcomes listed above
- Requires inpatient hospitalization or prolongation of existing hospitalization,
- Note that hospitalizations for the following reasons should not be reported as serious adverse events:
 - Routine treatment or monitoring of the studied indication, not associated with any deterioration in condition
 - Elective or pre-planned treatment for a pre-existing condition that is unrelated to the indication under study and has not worsened since signing the informed consent
 - Social reasons and respite care in the absence of any deterioration in the patient's general condition
- Note that treatment on an emergency outpatient basis that does not result in hospital admission and involves an event not fulfilling any of the definitions of a SAE given above is not a serious adverse event

Progression of underlying malignancy is not reported as an adverse event if it is clearly consistent with the suspected progression of the underlying cancer as defined by RECIST or

irRC. Hospitalization due solely to the progression of underlying malignancy should NOT be reported as a serious adverse event.

Clinical symptoms of progression may be reported as adverse events if the symptom cannot be determined as exclusively due to the progression of the underlying malignancy, or does not fit the expected pattern of progression for the disease under study.

Symptomatic deterioration may occur in some patients. In this situation, progression is evident in the patient's clinical symptoms, but is not supported by the tumor measurements. Or, the disease progression is so evident that the investigator may elect not to perform further disease assessments. In such cases, the determination of clinical progression is based on symptomatic deterioration. These determinations should be a rare exception as every effort should be made to document the objective progression of underlying malignancy.

If there is any uncertainty about an adverse event being due only to the disease under study, it should be reported as an AE or SAE.

8.2.2 Reporting

To ensure patient safety, every SAE, regardless of suspected causality, occurring after the patient has provided informed consent and until at least 150 days after the patient has stopped study treatment must be reported to Novartis within 24 hours of learning of its occurrence (90 days for patients who stopped PDR001 and continued MCS110 alone for more than 60 days).

If a patient starts a post treatment antineoplastic therapy, then only SAEs suspected to be related to study treatment will be reported.

Any SAEs experienced after this follow-up period should only be reported to Novartis if the investigator suspects a causal relationship to the study treatment. Recurrent episodes, complications, or progression of the initial SAE must be reported as follow-up to the original episode within 24 hours of the investigator receiving the follow-up information. An SAE occurring at a different time interval or otherwise considered completely unrelated to a previously reported one should be reported separately as a new event.

Information about all SAEs is collected and recorded on the Serious Adverse Event Report Form; all applicable sections of the form must be completed in order to provide a clinically thorough report. The investigator must assess and record the relationship of each SAE to each specific study treatment (if there is more than one study treatment), complete the SAE Report Form in English [For Japan only: complete the SAE report form in English or Japanese], and submit the completed form within 24 hours to Novartis. Detailed instructions regarding the submission process and requirements for signatures are to be found in the investigator folder provided to each site.

Follow-up information is submitted in the same way as the original SAE Report. Each re-occurrence, complication, or progression of the original event should be reported as a follow-up to that event regardless of when it occurs. The follow-up information should describe whether the event has resolved or continues, if and how it was treated, whether the blind was broken or not, and whether the patient continued or withdrew from study participation.

If the SAE is not previously documented in the Investigator's Brochure or Package Insert (new occurrence) and is thought to be related to the Novartis study treatment, an oncology Novartis

Chief Medical Office and Patient Safety (CMO&PS) department associate may urgently require further information from the investigator for Health Authority reporting. Novartis may need to issue an Investigator Notification (IN), to inform all investigators involved in any study with the same drug that this SAE has been reported. Suspected Unexpected Serious Adverse Reactions (SUSARs) will be collected and reported to the competent authorities and relevant ethics committees in accordance with Directive 2001/20/EC or as per national regulatory requirements in participating countries.

8.3 Pregnancies

To ensure patient safety, each pregnancy occurring while the patient is on study treatment must be reported to Novartis within 24 hours of learning of its occurrence. The pregnancy should be followed up to determine outcome, including spontaneous or voluntary termination, details of the birth, and the presence or absence of any birth defects, congenital abnormalities, or maternal and/or newborn complications. After the mother has provided consent, the newborn will be followed-up for 12 months.

Pregnancy should be recorded on a Clinical Trial Pregnancy Form and reported by the investigator to the oncology Novartis CMO&PS department. Pregnancy follow-up should be recorded on the same form and should include an assessment of the possible relationship to the investigational treatment and any pregnancy outcome. Any SAE experienced during pregnancy must be reported on the SAE Report Form.

For Korea only: Pregnancy outcomes should be collected for the female partners of any males who took study treatment in this study. Consent to report information regarding these pregnancy outcomes should be obtained from the mother.

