 17. Presence of \geq CTCAE Grade 2 toxicity (except alopecia, peripheral neuropathy and ototoxicity, which are excluded if \geq CTCAE Grade 3) due to prior cancer therapy.

18. Use of hematopoietic colony-stimulating growth factors (e.g. G-CSF, GM-CSF, M-CSF) \leq 2 weeks prior start or study drug. An erythroid stimulating agent is allowed as long as it was initiated at least 2 weeks prior to the first dose of study treatment.
19. Pregnant or lactating women, where pregnancy is defined as the state of a female after conception and until the termination of gestation, confirmed by a positive hCG laboratory test.
20. Women of child-bearing potential, defined as all women physiologically capable of becoming pregnant, unless they are using highly effective methods of contraception during dosing and for 150 days after the last dose of PDR001 or 90 days after the last dose of MCS110 for patients who stopped PDR001 and continued MCS110 alone for more than 60 days. Highly effective contraception methods include:
 - Total abstinence (when this is in line with the preferred and usual lifestyle of the patient. Periodic abstinence (e.g., calendar, ovulation, symptothermal, post-ovulation methods) and withdrawal are not acceptable methods of contraception)
 - Female sterilization (have had surgical bilateral oophorectomy with or without hysterectomy) total hysterectomy or tubal ligation at least 1.5 months before taking study treatment. In case of oophorectomy alone, only when the reproductive status of the woman has been confirmed by follow-up hormone level assessment
 - Male sterilization (at least 6 months prior to screening). For female patients on the study the vasectomized male partner should be the sole partner for that patient.
 - Use of oral, injected or implanted hormonal methods of contraception or placement of an intrauterine device (IUD) or intrauterine system (IUS), or other forms of hormonal contraception that have comparable efficacy (failure rate $<1\%$), for example hormone vaginal ring or transdermal hormone contraception.

In case of use of oral contraception women should have been stable on the same pill for a minimum of 3 months before taking study treatment.

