Women are considered post-menopausal and not of child bearing potential if they have had over 12 months of natural (spontaneous) amenorrhea with an appropriate clinical profile age appropriate (e.g. generally 40-59 years), history of vasomotor symptoms (e.g. hot flushes) in the absence of other medical justification or have had surgical bilateral oophorectomy (with or without hysterectomy), total hysterectomy, or tubal ligation at least 1.5 months ago. In the case of oophorectomy alone, only when the reproductive status of the woman has been confirmed by follow-up hormone level assessment is she considered not of child bearing potential.

21. For Korea only: Sexually active males unless they use a condom during intercourse while taking treatment and for 150 days after the last dose of PDR001 or 90 days after the last dose of MCS110 for patients who stopped PDR001 and continued MCS110 alone. They should not father a child in this period. A condom is required to be used also by vasectomized men in order to prevent delivery of the drug via seminal fluid.

6 Treatment

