
¹ Concomitant medications are only collected until 30 day of follow-up or the start of antineoplastic therapy, whichever comes first.
 
² Urine pregnancy test should be performed every month during and at the end of 150 days safety follow-up (90 days in case patient is only taking MCS110 alone, for more than 60 days).
 
⁴ Day 2, 4, 15 sampling times are only applicable to the Phase Ib part,
 
⁵ Cycles 5 and 6 only,
 
⁶ Only on C5D1
 
⁷ In reference to Section 7.1.5, the follow-up for safety, disease progression and survival will not be performed for patients who transfer to another clinical study to continue provision of study treatment or an alternative treatment option. For all other patients, the safety evaluation period will be completed but the disease-progression and survival follow up will not be performed.
																					

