7.2.2.5.7 Pregnancy

Pregnancy tests will be performed for women of child bearing potential per [Table 7-1](#).

At screening, a serum pregnancy test must be performed within 3 days before the first dose. During the study (Day 1 of each Cycle starting with Cycle 2), and at the End of Treatment visit, a serum pregnancy test must also be performed.

A urine pregnancy test should be performed every month during and at the end of the safety follow-up period (i.e. 150 days after the last dose of PDR001 or 90 days after the last dose of MCS110 for patients who stopped PDR001 and continued MCS110 alone for more than 60 days). If the patient is not coming to the clinic during the safety follow-up, it can be performed at home or at a local doctor's office, and the results will be communicated to the site staff. These follow-up pregnancy tests will be recorded only in the source documentation, not in the CRF.

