	Lactate dehydrogenase (LDH)	pH

A listing will be produced for the serum pregnancy test and only patients with positive test results will be included.

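### Section 8.3 ties pregnancy reporting to time on study treatment and no other passage extends it, although the protocol's contraception, testing and safety windows run to 150 days after PDR001

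*Protocol*

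**What the plan says.** **Reporting.** Protocol Section 8.3 says that "each pregnancy occurring while the patient is on study treatment must be reported to Novartis within 24 hours of learning of its occurrence". The next sentences, on determining the outcome and following the newborn for 12 months, refer to that pregnancy. The sentence on the Clinical Trial Pregnancy Form has no time limit of its own.

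**Contraception.** Exclusion criterion 20 (Section 5.3) excludes women of child-bearing potential "unless they are using highly effective methods of contraception during dosing and for 150 days after the last dose of PDR001". The alternative is 90 days after MCS110 for patients who stopped PDR001 and stayed on MCS110 alone for more than 60 days.

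**Testing.** Section 7.2.2.5.7: "A urine pregnancy test should be performed every month during and at the end of the safety follow-up period". The footnote to Table 7-1 repeats this.

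**Recording.** Section 7.2.2.5.7 adds: "These follow-up pregnancy tests will be recorded only in the source documentation, not in the CRF". Table 7-1, however, gives the pregnancy test category D, which Section 7.1 defines as entered in the clinical database, and marks it at the safety follow-up.

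**Output.** SAP Section 2.8.3: "A listing will be produced for the serum pregnancy test and only patients with positive test results will be included". SAP Section 2.3.2, on demographics, also says that pregnancy test results will be listed.

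**The concern.** The protocol treats the months after the last dose as a period in which pregnancy should be prevented and looked for. Section 11.3 tells women that the study medication may carry unknown fetal risks. The reporting rule does not name those months. If a woman conceives after her last dose and a monthly follow-up test finds it, the result reaches the site, but no stated rule carries it to the sponsor or starts outcome follow-up.

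At stake is the completeness of the pregnancy record for two investigational antibodies. If only complications reach the sponsor through the SAE route, uneventful outcomes are missing and there is no denominator.

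**Working it through.** The plan gives no figure on this point to reproduce. The check compares passages, with simple subtraction.

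**1. Windows side by side**

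| Activity | Where | Runs to |
|---|---|---|
| Pregnancy report, outcome and newborn follow-up | Protocol 8.3 | pregnancies occurring on study treatment; no later period named |
| Contraception, women | Protocol 5.3, criterion 20 | 150 days after PDR001 (90 after MCS110 if alone for more than 60 days) |
| Monthly urine test | Protocol 7.2.2.5.7, Table 7-1 footnote | same |
| AE collection | Protocol 8.1.1 | same |
| SAE reporting | Protocol 8.2.2 | 150 days after stopping study treatment (90 in the MCS110-alone case) |

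**2. Does another passage extend the duty?** Sections 7.1.3, 7.1.5, 7.2.2.5.7, 8.1.1, 8.2.1 and 8.2.2 do not require a report of a pregnancy that begins after treatment. In 8.2.1, pregnancy itself is not a seriousness criterion; a congenital anomaly is.

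**3. Size of the gap.** Uncovered days = window minus days counted as on treatment.
- Literal reading: 150 − 0 = 150 days; MCS110 alone, 90 − 0 = 90 days.
- Widest reading in the documents (last dose + 30 days, Protocol 10.4.2.1.2 and SAP 2.8): 150 − 30 = 120 days, 120/150 = 80%; MCS110 alone, 90 − 30 = 60 days, 60/90 = 67%.

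**4. SAE route.** Within the window, a pregnancy-related event that meets an SAE criterion is reportable, but only if suspected to be related once new antineoplastic therapy has started. After the window, it is reportable only if causality is suspected (8.2.2). A birth following conception in these months would usually fall after the window.

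**5. Data route.** The last scheduled serum test is at end of treatment; follow-up tests are urine. The serum listing in SAP 2.8.3 therefore does not reach them, and no listing can show urine results if 7.2.2.5.7 prevails over Table 7-1.

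**6. Wording of the window (separate, minor).** Let T be the days from the last PDR001 dose to the last MCS110-only dose.
- With the 60-day condition (criterion 20; Sections 4.3, 6.3.2, 8.1.1, 8.2.2): counted from PDR001, criterion 20 ends at day 150 if T ≤ 60, otherwise at T + 90, which exceeds 60 + 90 = 150.
- Whichever is longer (Sections 4.1 and 7.1.5): the larger of 150 and T + 90, which gives the same end day.
- Criterion 21 (Korea only), whose alternative is "90 days after the last dose of MCS110 for patients who stopped PDR001 and continued MCS110 alone" with nothing further: T + 90. One dose, 21 + 90 = 111 (150 − 111 = 39 days earlier). Two doses, 42 + 90 = 132 (150 − 132 = 18 days earlier). Three doses, 63 + 90 = 153.
- SAP 2.8 gives 150 days for PDR001 and 90 for MCS110, with neither qualifier.

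**The case against.** The strongest reply is that the reporting rule is broader than it looks. Section 8.3 does not say that only on-treatment pregnancies are reportable. Its pregnancy-form sentence and its sentence on SAEs during pregnancy carry no time limit, so a site could report a later pregnancy. That stands as a possible reading, but nothing in the text directs it, and both sentences follow the on-treatment one.

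A reader might infer several stronger things that the documents do not support:
- **That any pregnancy found in follow-up escapes reporting.** The rule turns on when the pregnancy occurs, and the 24 hours run from learning of it. One that began on treatment and is detected later is already covered.
- **That a post-treatment pregnancy appears in no output.** Appendix 1 (14.1.4.3) allows pregnancy as a study-phase completion reason, and SAP 2.3.1 tabulates reasons for leaving post-treatment follow-up. SAP 2.3.2 might also capture it, though it may mean baseline tests. None of these is pregnancy reporting or follow-up.
- **That follow-up tests are definitely kept out of the database.** Table 7-1 says the opposite of 7.2.2.5.7.
- **That no one need act.** The SAE duties in 8.2.2 apply, and home test results go to site staff.
- **That criterion 21 is the one passage without the 60-day condition.** Sections 4.1, 7.1.5 and SAP 2.8 also lack it.

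Numbers are small too. Amendment 05 states that enrollment is closed and 6 patients remained on treatment on 08-Jul-2019. Patients who transfer to another study or treatment option have no safety follow-up here (7.1.5). This limits the expected number of cases; it does not close the gap.

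**Conclusion.** The point holds as a mismatch of periods. Required pregnancy reporting and follow-up stop with study treatment, while contraception, monthly testing and AE/SAE collection continue. The uncovered time is up to 150 days per woman of child-bearing potential on the literal reading, and 120 of 150 days (60 of 90 for MCS110 alone) on the most generous definition of on treatment in the documents. That definition was written for analysis; applying it to 8.3 is an assumption.

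The documents do not give the number of women of child-bearing potential, so no count of affected pregnancies can be offered; few are likely. The correction still matters because it concerns safety and needs only aligned wording.

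The varying wording of the window is a lesser matter. The 111- and 132-day results assume MCS110-only doses on the 21-day schedule and concern men in Korea, for whose partners 8.3 collects outcomes without an on-treatment limit.

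**What to change.** 1. **Protocol 8.3:** state the period for reporting and outcome follow-up so that it matches the safety follow-up window already used in criterion 20 and Section 8.2.2. Criterion 20 counts from the last PDR001 dose and 8.2.2 from stopping study treatment, so name one starting point.
2. **Protocol 7.2.2.5.7 and Table 7-1:** resolve whether follow-up tests enter the clinical database. Either way, state that a positive follow-up test is reported on the existing Clinical Trial Pregnancy Form.
3. **SAP:** list pregnancies reported on treatment and in follow-up from whichever source holds them. Asking only for a urine-test listing would fail while 7.2.2.5.7 keeps those results out of the CRF.
4. **Separately:** reconcile the window wording across criteria 20 and 21, Protocol Sections 4.1, 4.3, 6.3.2, 7.1.5, 8.1.1 and 8.2.2, and SAP 2.8. Which contraception period applies is for the sponsor to settle.

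The cost is a few sentences, one SAP listing and a small number of extra reports. The tests and the form already exist. If the sponsor decides that follow-up results belong in the database, CRF collection for those tests is an added cost.
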